**Table 2: Dose Modifications**

NCI CTC Toxicity Grade	Dose Modification Instructions (also see Instructions for Initiation of a New Cycle above)
Hyperthyroidism or hypothyroidism	
 
• Omit lenalidomide for remainder of cycle, evaluate etiology, and initiate appropriate therapy.
 
• See Instructions for Initiation of a New Cycle and reduce the dose of lenalidomide by 1 dose level*.
 

other non-hematologic toxicity <math>\geq</math> Grade 3	
 
• Hold (interrupt) lenalidomide dose. Follow at least weekly.
 
• If the toxicity resolves to <math>\leq</math> grade 2 prior to the scheduled end of the current cycle, restart lenalidomide and continue through the scheduled end of the current cycle. Otherwise, omit for remainder of cycle. Omitted doses are not made up. For toxicity attributed to lenalidomide, reduce the lenalidomide dose by 1 dose level when restarting lenalidomide.
 

#### 5.5.3.7 Treatment adherence

Research center personnel will review the dosing instructions with subjects. Subjects will be asked to maintain a diary to record lenalidomide administration. Subjects will be asked to bring any unused lenalidomide and empty drug containers to the research center at their next visit. Research personnel will count and record the number of used and unused drug at each visit and reconcile with the patient diary.

Any unused Revlimid® (lenalidomide) should be returned to the patient for disposition in accordance with the REMS® program.

### 5.6 Concomitant therapy

#### 5.6.1 Recommended concomitant therapy

Subjects should receive full supportive care, including transfusions of blood and blood products, antibiotics, hematopoietic growth factors, analgesics, and antiemetics when appropriate.

**5.6.1.1 Tumor Lysis Syndrome (TLS) Prophylaxis (allopurinol and hydration)**

Tumor lysis syndrome (TLS), characterized by hyperkalemia, hyperuricemia, and hyperphosphatemia resulting from the rapid release of potassium, uric acid, and phosphate, has been reported in CLL patients treated with lenalidomide necessitating TLS prophylaxis including allopurinol and oral hydration. The risk of TLS is highest during the first cycle of therapy and decreases after resolution of lymphocytosis. Allopurinol 300mg po daily will be given at the beginning at least 3 days before cycle 1 and continuing through the end of cycle 1. TLS prophylaxis is required for all subjects in cycle 1. It can be considered prior to initiation of lenalidomide in subsequent cycles at the discretion of the investigator. Subjects should be instructed to maintain adequate hydration and maintain urinary output as an additional measure to prevent TLS. To maintain fluid intake, subjects should be instructed to drink 8 to 10 eight ounce glasses of water each day for the first 14 days of Cycle 1. Hydration levels should be adjusted according to age and clinical status, and lowered if the subject's cardiovascular status indicates the possibility of volume overload. Based on clinical and laboratory parameters, TLS prophylaxis may be continued or restarted as needed at the Investigator's discretion.

**5.6.1.2 Anticoagulation Consideration**

Lenalidomide increases the risk of thrombotic events in patients who are at high risk or with a history a thrombosis, in particular when combined with other drugs known to cause thrombosis. When lenalidomide is combined with other agents such as steroids (e.g. dexamethasone, prednisone), anthracyclines (Doxil, Adriamycin) and erythropoietin the risk of thrombosis is increased. For information on the risk of venous thromboembolism with combined oral contraception see Appendix: Risks of Fetal Exposure, Pregnancy Testing Guidelines and Acceptable Birth Control Methods.

All patients should receive prophylactic anti-coagulation. Aspirin (81 or 325 mg) is the recommended agent for anti-coagulation prophylaxis. Low molecular weight heparin

---

may be utilized in patients that are intolerant to ASA. Coumadin should be used with caution and close monitoring of INR.

Patients with a history of venous thromboembolism should be closely monitored throughout the study, especially during periods of fluctuating platelet counts.

Prophylactic anti-coagulation should be held for platelet counts < 50,000/mm^3 and then restarted when platelet counts are above this level.

Full therapeutic anti-coagulation should be considered for patients who have a history of venous thromboembolism.

#### **5.6.1.3 Treatment and Dose Modification for Tumor Lysis Syndrome**

All subjects meeting criteria of laboratory TLS or  $\geq$  Grade 1 TLS according to the Cairo-Bishop Definition of Tumor Lysis Syndrome (see Appendix) should receive vigorous intravenous hydration and should be considered for rasburicase therapy as needed to reduce hyperuricemia, until correction of electrolyte abnormalities.

#### **5.6.1.4 Tumor Flare Reaction (TFR):**

Prophylaxis for (TFR) is not recommended. Grade 1 TFR may be treated with NSAIDs (i.e. ibuprofen 400-600 mg orally every 4-6 hours as needed). TFR  $\geq$  Grade 2 may be treated with corticosteroids. Narcotic analgesics may be added as needed for pain control in subjects experiencing  $\geq$  Grade 2 tumor flare. If corticosteroids are used, the following dosage schedule is recommended; prednisone 20mg PO QD x 7 days followed by 10mg PO QD x 7 days.

Tumor flare occurring during the first 2 weeks of Cycle 4 of treatment protocol should be recorded as an adverse event and not as progressive disease (PD). For tumor flare occurring after the first 2 weeks of Cycle 4 of treatment protocol, differentiate tumor flare from progression.

**5.6.1.5 Prophylaxis of infections**

Patients will receive prophylaxis for *Pneumocystis carini* pneumonia with trimethoprim-sulfamethoxazole or equivalent, prophylaxis for herpes virus with acyclovir 400mg twice per day or equivalent and antifungal prophylaxis with fluconazole 100mg daily or equivalent. Prophylaxis will be administered throughout the treatment period until end of cycle 5.

**5.6.1.6 Growth Factor Support**

Patients may receive growth factor support in the form of granulocyte colony stimulating factor (G-CSF), granulocyte macrophage colony stimulating factor (GM-CSF), or erythropoietin at the discretion of the treating physician.

**5.6.2 Prohibited concomitant therapy**

Concomitant use of other anti-cancer therapies, including radiation, thalidomide, or other investigational agents is not permitted while subjects are receiving protocol therapy during the treatment phase of the study.

**5.7 Discontinuation of Study Treatment (See Also Section 5.5.3.5 and 5.5.3.6)**

Treatment will continue as per dosing schema. Treatment will be discontinued at the occurrence of any of the following events.

- Disease progression
- Adverse event(s) that, in the judgment of the Investigator, may cause severe or permanent harm or which rule out continuation of the treatment regimen.
- Discontinuation of treatment protocol for any reason.
- Major violation of the study protocol.
- Withdrawal of consent
- Lost to follow up

---

- Death
- Pregnancy or a positive pregnancy test

### **5.8 Lenalidomide Maintenance Therapy (MT)**

Per protocol Section 5.5, subjects who do not achieve a CR by Cycle 12 may continue lenalidomide single agent until disease progression or unacceptable toxicities. Any subject completing 12 cycles of protocol therapy may begin Lenalidomide Maintenance Therapy (MT).

During MT the following study procedures will be initiated:

1. The subject will have a safety CBC with differential and CMP every four weeks which will not be recorded in the database.
2. Physical examinations will be at the discretion of the investigator or per standard of care. The physical exam results will not be recorded in the database.
3. For the purpose of the study, vital signs, weight, and concomitant medications are not required to be recorded in the database.
4. No subject pill diary or source documentation of dosing will be maintained. The patient report of daily dosing will be sufficient to document adherence.
5. The only adverse events collected and entered into the database will be grade 3 or grade 4 cytopenias.
6. All standard of care guidelines as outlined by the Celgene Corporation for lenalidomide administration, including prophylactic anticoagulation, pregnancy prevention, and counseling through the Revlimid REMS program will continue to be followed.
7. Serious adverse events will be collected and reported as outlined in section 6.
8. A bone marrow biopsy and CT scan will be performed every six months for two years. After this time point, these tests need only be performed at the discretion of the treating physician.

At the discretion of the investigator:

Amendment 5 Dated 03/02/2016

---

1. Lenalidomide dose may be maintained at the subject's current dose or if previously dose reduced, may be escalated to the maximum of 10 mg daily.
2. Lenalidomide dose reductions may be initiated to 5 mg daily or 5 mg every other day.

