## 2 Schedule of Study Assessments \*

Procedure	All visits/assessments may be scheduled $\pm$ 3 business days										
	Screening  <math>\leq</math> 28 days from Baseline (First day drug administration)	Cycle 1	Cycles 2 - 3	Cycle 4 				Cycles 5-12	Lenalidomide Maintenance Therapy	Discontinuation From Protocol Therapy 	Follow- Up Phase
	Days 1, 8, 15, and 22	Days 1, and 15	Day 1	Day 3 or 4 at investigator discretion	Day 8	Day 15	Day 22	Day 1 and 15			
Study drug administration **		X	X	X					X	X	
Record prior medications, treatments	X										
Record prior anti-cancer therapies	X										
Physical examination, vital signs, weight	X	X 	X 	X 					X 		
ECOG performance status	X	X 	X 	X 					X 		
ECG	X										
Assess lymphadenopathy, spleen / liver 		X 	X 	X 		X 	X 		X 		
Peripheral blood for , ZAP 70, $\beta$ -2 microglobulin, and IgHV mutational status 	X										
Research samples 	X			X							
Baseline lesion assessment	X			X							
Bone marrow 	X			X					X	X	X 
CT of the neck, chest, abdomen & pelvis 	X			X					X		X 
Hematology 	X	X	X	X 		X 	X 	X 	X 	X 	
Serum chemistry 	X	X	X	X 	X 	X 	X 	X 	X 	X 	
Hepatitis B and C serology, HBV DNA PCR 	X 										
Pregnancy testing 	X			X		X	X	X	X		
Register patient into REMS® program	X										

Prescribe lenalidomide via REMS 				X				X			
Record adverse events 		X	X	X				X	X 		
Record concomitant therapies/procedures		X	X	X				X			
Obtain Follow-Up anti-cancer treatments											X
Obtain Follow-Up survival information											X

\* An unscheduled visit can occur at any time during the study. Source must be maintained for these unscheduled visits. The date for the visit and any data generated must be recorded on the appropriate CRF. Source documents for these unscheduled visits must also be maintained.

\*\* See Table 1 for detailed study drug administration schedule.

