 Physical examination of lymphadenopathy, the spleen and liver will be performed on Days 1 and 15 of Cycle 1 to access for tumor flare reaction, and on Day 1 of subsequent cycles to assess response.

 Peripheral blood for ZAP 70 IgVH mutational status, beta-2 microglobulin analyses will be done only at screening. If ZAP 70, IgVH and beta-2 microglobulin was performed within 6 months of screening date, it is not necessary to repeat at screening. Research samples for storage will be drawn during screening, day 1 of cycle 4, day 1 of Maintenance Therapy or discontinuation from protocol therapy if earlier than the end of cycle 12.

 Bone marrow studies will be performed for all subjects at baseline, at the end of cycle 3 (day 21-28 prior to cycle 4), after completion of cycle 12 and every 6 months afterwards during lenalidomide maintenance therapy for two years. Bone marrow studies at any other time point will be performed at the physician's discretion.

 CT of the neck, chest, abdomen & pelvis will be performed at screening, for response assessment at the end of cycle 3 (day 21-28 prior to cycle 4), after the end of cycle 12 (7-10 days after discontinuation of lenalidomide) and every 6 months afterwards during lenalidomide maintenance therapy for two years. After any other time point, CT scans will be performed at the physician's discretion.

 Hematology – CBC with differential WBC and platelet counts. Hematology profiles are required weekly during Cycle 4 (which corresponds to Cycle 1 of lenalidomide-containing therapy), and during any cycle in which the dose of lenalidomide is escalated or re-escalated. For subjects who are on a stable lenalidomide dose (without dose escalation or interruption of the planned dosing schedule) for  $\geq 1$  cycle of treatment, hematology profiles are required on Days 1 and 15 of the cycle.

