 Chemistry includes sodium, potassium, chloride, CO2, calcium, magnesium, phosphorus, BUN, creatinine, glucose, albumin, total protein, alkaline phosphatase, total bilirubin, AST/SGOT, ALT/SGPT, LDH, and uric acid. At a minimum, for tumor lysis syndrome (TLS) monitoring purposes, subjects will have chemistry assessments weekly during at least the first 2 cycles of lenalidomide-containing treatment. Chemistry assessments on Day 3 or 4 of Cycle 1 of lenalidomide-containing treatment are at the investigator's discretion. In addition, because the risk for TLS may be elevated when lenalidomide is re-started after treatment interruptions or when the lenalidomide dose is escalated, in any cycle in which the lenalidomide dose is escalated or re-escalated or treatment is interrupted for more than 1 week, subjects may need to have weekly chemistry assessments performed for at least 4 consecutive weeks as well as an additional chemistry assessment on day 3 or 4 during the first week of escalating, re-escalating or re-initiating lenalidomide therapy. If TLS occurs, subjects will have additional chemistry assessments weekly for at least 4 consecutive weeks as well as on Day 3 or Day 4 following re-initiation of lenalidomide. For subjects who do not experience any abnormalities in serum chemistry assessments for 2 consecutive cycles while on a stable lenalidomide dose (without dose escalation or interruption of the planned dosing schedule) throughout these 2 cycles, the timing of chemistry assessments may be reduced to Day 1 and Day 15 in subsequent cycles. See section 5.6.1.1 for TLS prophylaxis instructions. To include Thyroid Stimulating Hormone (TSH) at Screening, at treatment discontinuation, and whenever clinically indicated. T3 and T4 levels may be assessed as clinically indicated.

 Hepatitis B Virus DNA by PCR will be tested at screening. If it is positive then it will be tested every 2 weeks during cycle 1, every 4 weeks during cycles 2 ad 3, and then every 2 to 3 months thereafter.

---

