 Cycle 4 may begin up to 14 days after cycle 3 bone marrow biopsy to allow for results of response assessments to be available.

 CBC and CMP only every 4 weeks. See Section 5.8. Any grade 3 or 4 cytopenia will be recorded as an adverse event during Maintenance Therapy. No other adverse events will be recorded during Maintenance Therapy

 Upon discontinuation of study therapy, any diagnostic testing will be at the discretion of the physician.

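### Maintenance schedules blood counts every 4 weeks with no stated exception after a lenalidomide dose increase, at odds with the weekly rule in schedule footnote 5

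*Combined protocol and SAP*

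**What the plan says.** Section 5.8 governs lenalidomide after cycle 12. At the investigator's discretion the current dose may be kept or, "if previously dose reduced, may be escalated to the maximum of 10 mg daily". Item 1 of the same section sets the laboratory schedule: "The subject will have a safety CBC with differential and CMP every four weeks". In the Section 2 schedule table, the maintenance cell of the hematology row is marked with footnote 14, which reads "CBC and CMP only every 4 weeks" and points back to Section 5.8. Neither place mentions what happens after a dose increase.

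Footnote 5 of the same table requires weekly hematology in Cycle 4 and "during any cycle in which the dose of lenalidomide is escalated or re-escalated". It relaxes this only for patients on a stable dose, for whom "hematology profiles are required on Days 1 and 15 of the cycle". Footnote 5 is marked on the hematology row label and on the Cycle 4 and Cycles 5-12 cells, but not on the maintenance cell.

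Three other provisions bear on the point. Item 6 of Section 5.8 keeps in force "All standard of care guidelines as outlined by the Celgene Corporation for lenalidomide administration". The general note to the schedule states that "An unscheduled visit can occur at any time during the study". For chemistry, footnote 6 is permissive after an escalation: "subjects may need to have weekly chemistry assessments performed for at least 4 consecutive weeks".

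**The concern.** Footnote 5 treats a lenalidomide increase as a reason to count weekly. The maintenance text allows the same kind of increase but does not say that the weekly rule comes with it. A site working from the maintenance column would find only the 4-weekly interval.

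The clause applies to patients whose dose was reduced earlier. Table 2 of Section 5.5.3.6 reduces the dose for platelets below 25,000/mm³ and, where colony-stimulating factors are not used, for second and later qualifying neutropenia episodes. Some of these patients may therefore have been reduced for cytopenia.

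Two safety actions depend on having a count. Table 2 holds lenalidomide for grade 4 neutropenia, for febrile grade 3 neutropenia and for platelets below 25,000/mm³. Table 2 and Section 5.6.1.2 hold prophylactic anticoagulation below 50,000/mm³, and Section 5.8 item 6 continues that anticoagulation in maintenance. Physical examinations are discretionary in maintenance (item 2), so the blood test is the main scheduled safety check. Apart from serious events, grade 3 and 4 cytopenias are also the only adverse events collected in this phase (items 5 and 7), and finding them depends on when counts are taken.

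**Working it through.** The plan states no figure for this interval, so there is none to reproduce. The check is a count of scheduled visits under each rule.

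Inputs:
- Footnote 5, escalation rule: every 7 days.
- Footnote 5, stable-dose rule: Days 1 and 15 of a 28-day cycle.
- Section 5.8 item 1 and footnote 14: every 28 days.
- All days are nominal; the schedule allows ±3 business days.

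Take an increase on day 1, on the same day as a scheduled count, and list the later counts through day 29.

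| Rule | Scheduled counts | First gap | Counts through day 29 | Counts before day 29 |
|---|---|---|---|---|
| Weekly (footnote 5, escalation) | days 8, 15, 22, 29 | 8 − 1 = 7 days | 4 | 3 |
| Days 1 and 15 (footnote 5, stable dose) | days 15, 29 | 15 − 1 = 14 days | 2 | 1 |
| Every 4 weeks (maintenance) | day 29 | 29 − 1 = 28 days | 1 | 0 |

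If the increase comes k days after the last 4-weekly count, the gap to the next one is 28 − k days. Its maximum is 28 days, at k = 0. Against the weekly rule, the first count is then up to 28 − 7 = 21 days later, and 4 − 1 = 3 scheduled counts are absent.

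A patient just escalated in maintenance thus has fewer scheduled counts (1) than a stable patient in cycles 5-12 (2). Part of that difference is the general step-down in maintenance. The comparison that isolates the escalation rule is 1 against 4.

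Could another provision supply the earlier count?
- Table 2 calls for weekly counts, but only once a count has already triggered a hold. It cannot supply the first one.
- Unscheduled visits are permitted, not required.
- Item 6 of Section 5.8 names anticoagulation, pregnancy prevention and counseling as examples. It does not mention count timing, and the guidelines it refers to are not in the documents.

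Effect on the main analysis: Section 10.1 places the primary response assessment at the end of cycle 3. Lenalidomide starts in cycle 4 and maintenance follows cycle 12, so nothing here can alter the primary endpoint, alpha or power.

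**The case against.** The strongest reply is that the weekly rule already applies. Footnote 5 is worded for any cycle and is marked on the row label, which spans the maintenance column. Section 5.5.3.3 places treatment beyond cycle 12 within the same dosing section, so maintenance can be read as further cycles. The word restricting footnote 14 may limit which tests are done rather than how often. This reading is tenable, and it is why the point is a conflict or ambiguity and not a proven contradiction. It does not remove the problem: the footnote on the maintenance cell is the more specific one, and it sends the reader to a section with no exception.

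The second reply is that lighter monitoring is deliberate. Section 5.8 cuts laboratory tests, examinations, diaries and adverse event capture together, for patients who have completed cycles 4 to 12. Escalation is discretionary, Section 10.5 asks for close toxicity monitoring throughout, and nothing stops an investigator from ordering an earlier count. This stands as an explanation of 4-weekly counts on a stable dose. It does not explain dropping the escalation rule while still permitting escalation.

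The third reply is that the manufacturer's guidelines under item 6 may set the timing. That cannot be excluded from the documents.

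A reader might infer that 28 days is the usual gap, because Section 5.5.3.6 puts increases at the start of a new cycle. The documents do not support this. It would apply the cycle-based dosing rule to maintenance while denying the same reach to footnote 5, and no text ties maintenance counts to the day of an increase. Twenty-eight days is the maximum. A reader might also infer that the one-level and qualifying-cycle rules for re-escalation (Sections 5.5.3.4 and 5.5.3.6) are missing in maintenance. They are worded generally and can be read to apply already.

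**Conclusion.** The point holds as a gap in safety scheduling that should be fixed, with moderate confidence. On the literal maintenance rule, the first scheduled count after an increase can come up to 28 days later instead of 7, with 1 scheduled count instead of 4 through day 29. This assumes nominal visit days, an increase coinciding with a 4-weekly count, and no earlier count required by the manufacturer's guidelines.

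The figures measure time without a scheduled count. They are not a probability of harm. The documents do not say how many maintenance patients are on a reduced dose, how many were reduced for cytopenia, or how often counts fall after an increase.

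**What to change.** Amend footnote 14 and Section 5.8 item 1 to read: every 4 weeks, except weekly CBC (as in footnote 5) for the 28 days after any lenalidomide dose increase. Chemistry after an increase can stay a matter of judgment, as footnote 6 has it. If the intention is that footnote 5 already applies, the same wording serves as clarification.

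The cost is about three extra blood draws per escalation (days 8, 15 and 22), plus the amendment process of Section 8.1: the principal investigator's agreement, review by both supporting companies and written ethics approval. Sample size, primary endpoint, dosing rules and database entry do not change.

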### **5.9 Follow-Up**

If a subject discontinues study treatment at any time during cycles 1-12, “Discontinuation from Protocol Therapy” on the Schedule of Assessments, Section 2 will be performed. If the bone marrow biopsy and CT scans have been performed in the past 28 days to determine progression of disease, it is not necessary to repeat them.

The subject will then enter the follow-up period unless consent is withdrawn. If a subject enters Maintenance Therapy (MT) after cycle 12, the follow-up period will begin after discontinuation of lenalidomide in MT. If a subject completes 12 cycles and does not enter MT, follow-up will begin at the completion of cycle 12.

